6.3 Pharmacokinetic Variables

Not applicable.

6.4 Pharmacodynamic Variables

Not applicable.

6.5 Other Variables

- The duration of exposure

For each subject, the duration of exposure will be calculated in days, using the following formula:

$$(\text{'Date last dose of study drug'}^{\#} - \text{'Date first dose'}^*) + 1$$

- Dose Intensity

Dose Intensity will be examined for subjects in the safety population whose total capsule count is known. Number of capsules which should have been taken depends on the number of days between the date of last and first capsule taken, including both daytimes (further details are given in the Tables Manual):

[Total number of capsules consumed by subject]

----- x 100

[Total number of capsules subject should have taken]

Where, total number of capsules consumed will be calculated as:

(total number of capsules dispensed) – (total number of capsules returned).

Where total number of capsules should have taken will be calculated by duration of exposure times 4.

Previous and concomitant medication

Previous medication is defined as medication with at least one dose taken before the date of the first dose of study drug.

Concomitant medication is defined as medication with at least one dose taken between the date of first dose (inclusive) and the date of last dose (inclusive) of study drug.

7 STATISTICAL METHODOLOGY

7.1 General Considerations

For continuous variables, descriptive statistics will include the number of subjects (n), mean, standard deviation, median, minimum and maximum. When needed, the use of other percentiles (e.g., 10%, 25%, 75% and 90%) will be mentioned in the relevant section.

Frequencies and percentages will be displayed for categorical data. Percentages by categories will be based on the number of subjects with no missing data, i.e., will add up to 100%.

All data processing, summarization, and analyses will be performed using SAS® Version 9.1.3 or higher on Unix. Specifications for table, figures, and data listing formats can be found in the TLF specifications for this study.

For the definition of subgroups of interest please refer to Section 7.8

7.2 Study Population

7.2.1 Disposition of Subjects

The following subject data will be presented:

- Number of subjects with informed consent, discontinued before first dose of study medication;
- Number and percentage of subjects in each analysis set;
- Number and percentage of subjects completed and discontinued treatment, by primary reason for treatment discontinuation;
- Number and percentage of subjects completed and discontinued the study, by primary reason for study discontinuation;

7.2.2 Protocol Deviations

Protocol deviations as defined in the study protocol (Section 8.1.6 Protocol Deviations) will be assessed for all dosed patients. The number and percentage of subjects meeting any criteria will be summarized for each criterion and overall. Subjects deviating from a criterion more than once will be counted once for the corresponding criterion. Any subjects who have more than one protocol deviation will be counted once in the overall summary. A data listing will be provided by site and subject.

The protocol deviation criteria will be uniquely identified in the summary table and listing. The unique identifiers will be as follows:

- PD1 - Entered into the study even though they did not satisfy entry criteria,
- PD2 - Developed withdrawal criteria during the study and was not withdrawn,
- PD3 - Received wrong treatment or incorrect dose,
- PD4 - Received excluded concomitant treatment.

7.2.3 Demographic and Other Baseline Characteristics

Demographic and other baseline characteristics that have been collected on the eCRF will be summarized by descriptive statistics.

Number and percentage of subjects randomized in each country and site will be presented.

Descriptive statistics for:

Baseline and demographic characteristics:

- 1) Age (Informed consent date- DOB+1)/365.25
- 2) Race
- 3) Ethnicity
- 4) Screening ECG
- 5) Weight

- 6) ECOG Status
- 7) Measureable disease (y/n)
- 8) Number of bone lesions at screening
- 9) Disease sites at screening

Disease History;

- 1) Time from initial diagnosis to informed consent date (Informed consent date- Initial dx date+1)/365.25
- 2) Primary Gleason score at initial diagnosis
- 3) Secondary Gleason score at initial diagnosis
- 4) Total Gleason score at initial diagnosis
- 5) PSA result at initial diagnosis
- 6) Primary tumor assessment at initial diagnosis
- 7) Pathologic tumor stage at initial diagnosis
- 8) Clinical lymph node stage at initial diagnosis
- 9) Pathological lymph node stage at initial diagnosis
- 10) Distant metastasis at initial diagnosis
- 11) Anatomic staging at initial diagnosis
- 12) Time from CRPC diagnosis to informed consent date (Informed consent date- CRPC dx date+1)/365.25
- 13) CRPC diagnosis criteria
- 14) Time from initial diagnosis of metastasis to informed consent date (Informed consent date- Metastasis dx date+1)/365.25

Prior Radiation:

- 1) Prior radiation therapy (y/n)
- 2) Type of prior radiation therapy
- 3) Area radiated

Prior Procedures:

- 1) Any prior procedures (y/n)
- 2) Type of prior procedures

This will be done for FAS.

Medical history is coded in MedDRA, and will be summarized by System Organ Class (SOC) and Preferred Term (PT) as well as by PT alone (in descending order) for the FAS.

7.2.4 Previous and Concomitant Medications

Previous medications are coded with WHO-DD, and will be summarized by therapeutic subgroup (ATC 2nd level) and chemical subgroup (ATC 4th level) and preferred WHO name for the SAF.

As with previous medication, concomitant medication will be summarized by therapeutic subgroup (ATC 2nd level) and chemical subgroup (ATC 4th level) and preferred WHO name for the SAF. Subjects taking the same medication multiple times will be counted once per medication and investigational period. A medication which can be classified into several chemical and/or therapeutic subgroups is presented in all chemical and therapeutic subgroups.

7.3 Study Drugs

7.3.1 Exposure

The following information on drug exposure will be presented for the SAF:

- Descriptive statistics for cumulative amount of the drug subject was exposed to and average daily dose; and
- Number and percent of subject with dose increases, decreases or interruptions.

Duration of exposure will be summarized in two ways.

- Descriptive statistics will be presented.
- Exposure time will be categorized according to the following categories:
 - less than or equal to 28 days
 - greater than 28 days, less than or equal to 84 days
 - greater than 84 days, less than or equal to 168 days
 - Greater than 168 days
 - Unknown.

Counts and percentages of subjects in each of these categories will be summarized for each for the SAF.

Counts and percentages of dose reductions, dose interruptions, and dose discontinuations will be presented.

7.3.2 Treatment Compliance

Overall compliance with the dosing schedule will be examined for subjects in the SAF whose total study drug count and first and last days of treatment are known.

Percent overall compliance will be summarized in two ways for the SAF:

- Descriptive statistics will be presented.
- Percent compliance will be categorized according to the following categories:

- less than 80%
- greater than or equal to 80% and less or equal to 120%
- greater than 120%

7.4 Analysis of Efficacy

7.4.1 Analysis of Primary Endpoint(s)

The primary analysis will be performed on the Radiographic progression-free survival (rPFS). rPFS will be summarized using descriptive statistics. The survival curve and the median will be estimated using the Kaplan-Meier method. A two-sided 90% confidence interval will be provided for these estimates by use of the Brookmeyer and Crowley method and will be reported along with the corresponding 90% CI.

The SAS code used to produce median from Kaplan-Meier estimates and corresponding 90% CI will be similar to that shown below:

```
proc lifetest data=adtte plots=(s) outsurv=surv;
  time survtime*censor(0);
  run;
```

An analysis of the primary endpoint will be conducted by subgroups.

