7.4.1 Analysis of Primary Endpoint

7.4.1.1 Primary Analysis

The primary efficacy endpoint, rPFS, will be analyzed using Kaplan-Meier methodology to account for censored outcomes (i.e. no observation of rPFS event within the study follow-up period).

Ninety percent (90%) confidence interval will be provided for the median rPFS.

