4 SAMPLE SIZE

Prior clinical trials data in the post-chemo setting have shown the following median rPFS for subject randomized to initial placebo, placebo+prednisone, or mitoxantrone+prednisone therapy:

- AFFIRM: Placebo = 2.9 months
- COU-301: Placebo + Prednisone = 3.6 months
- TROPIC: Mitoxantrone + Prednisone = 1.4 months

With a sample size of 40 subjects and an assumed median rPFS of 4 months for the therapy defined in this single-arm study, approximately 34 events are expected over a 12-month accrual and 12-month minimum follow-up. Further assuming uniform accrual, 10% loss to follow-up, and an exponential distribution for the rPFS event times, the expected lower bound of the 90% confidence interval for the median is approximately 2.5 months based upon simulations.

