6.1.2 Secondary Efficacy Endpoints

Time to PSA Progression

For patients with PSA declines, the PSA progression date is defined as the date that a $\geq 25\%$ increase and an absolute increase of $\geq 2 \mu\text{g/L}$ (2 ng/mL) above the nadir is documented, which is confirmed by a second consecutive value obtained 3 or more weeks later.

For patients with no PSA declines, the PSA progression date is defined as the date that a $\geq 25\%$ increase and an absolute increase of $\geq 2 \mu\text{g/L}$ (2 ng/mL) above the baseline is documented, which is confirmed by a second consecutive value 3 or more weeks later. Baseline is defined as last PSA measurement prior to first dose.

Time to PSA progression is defined as the PSA progression date minus date of first dose + 1, which will be censored in the following scenarios:

- If patient does not have any PSA progression, it will be censored at last PSA sample date.
- If patient does not have post baseline PSA assessment, it will be censored at Day 1.
- If patient took any new anti-cancer therapy before any PSA event, the time to PSA progression will be censored at the PSA sample date prior to the date of new anti-cancer therapy.

Overall Survival Rate at 1 Year

Overall Survival is defined date of death due to any cause minus date of first dose +1. If a patient has not died, overall survival is censored at the last known alive date.

The last known alive date will be derived based on the maximum of last known alive dates in the survival follow up CRF page, last visit, or last SAE onset date.

Overall survival rate at 1 year is defined as the corresponding Year 1 (Day 365) Kaplan-Meier estimate on survival curve.

Time to first use of a subsequent antineoplastic therapy

Time to first use of a subsequent antineoplastic therapy is defined as date of the first systemic antineoplastic therapy minus first dose date +1. If a patient has not started the antineoplastic therapy, the time to event analysis is censored at the last dose date of study medication.

PSA response

PSA response is defined in below categories:

- PSA30 (maximum decline of $\geq 30\%$ decline from baseline at lowest post baseline)
- PSA50 (maximum decline of $\geq 50\%$ decline from baseline at lowest post baseline)
- PSA90 (maximum decline of $\geq 90\%$ decline from baseline at lowest post baseline)

Objective response rate

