7.4.2 Analysis of Secondary Endpoints

Overall Survival, time to PSA progression, and time to first use of a subsequent antineoplastic therapy will be analyzed in the same manner as the primary endpoint.

PSA response rate (PSA30, PSA50, and PSA90) and objective response rate along with exact 90% confidence interval (Clopper-Pearson) will be calculated.

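### The specimen SAS code for the 90% interval on median rPFS sets no confidence level; run as printed under an assumed default alpha of 0.05, it would return 95% limits

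*SAP*

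**What the plan says.** The required level is clear in the text. Protocol 7.4.1.1 states: "Ninety percent (90%) confidence interval will be provided for the median rPFS". SAP 7.4.1, referring to the survival curve and the median, states: "A two-sided 90% confidence interval will be provided for these estimates by use of the Brookmeyer and Crowley method".

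SAP 7.4.1 then introduces a short code block: "The SAS code used to produce median from Kaplan-Meier estimates and corresponding 90% CI will be similar to that shown below". The procedure statement is "proc lifetest data=adtte plots=(s) outsurv=surv". It names an input data set, a plot and an output data set. The TIME statement that follows names the time and censoring variables. Neither statement sets a confidence level or an interval transform, and the SAP prints no other code that does.

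The same method reaches further:

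- SAP 7.4.2 says that overall survival, time to PSA progression and time to first subsequent antineoplastic therapy "will be analyzed in the same manner as the primary endpoint".
- SAP 6.1.2 reads the 1-year survival rate from the curve: "Overall survival rate at 1 year is defined as the corresponding Year 1 (Day 365) Kaplan-Meier estimate on survival curve".
- SAP 7.8 repeats rPFS and time to PSA progression in subgroups.
- SAP 7.4.3 asks for Kaplan-Meier medians with 90% intervals by biomarker status.

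The software is SAS "Version 9.1.3 or higher on Unix" (SAP 7.1).

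**The concern.** The only code shown for the primary interval does not contain the 90% that the surrounding text requires. A programmer who copies it gets whatever level the procedure uses by default. If that is 95%, the table would carry 95% limits under a 90% heading.

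This is a single-arm, descriptive trial. The interval on median rPFS is its main statement of precision, and SAP section 4 justifies the sample size by one such limit: "the expected lower bound of the 90% confidence interval for the median is approximately 2.5 months based upon simulations". A reported interval at another level could not be compared with that planning figure.

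One copied line could carry the error into all the time-to-event endpoints listed above. The medians depend on the level used for quartile limits. An interval for the 1-year survival rate depends on the level used for curve limits. These may be separate options in some SAS releases, and the SAP fixes only a minimum release, so setting one may not set the other.

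**Working it through.** **Inputs (SAP section 4).** N = 40, median rPFS 4 months, exponential times, uniform 12-month accrual, 12-month minimum follow-up, 10% loss. Stated results: about 34 events and an expected 90% lower limit of about 2.5 months. One assumption comes from outside the documents: the PROC LIFETEST default is alpha = 0.05.

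**Step 1: reproduce the event count.** Let λ = ln 2 / 4 = 0.1733 per month, with follow-up uniform on 12 to 24 months.

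- P(event) = 1 − (e^(−12λ) − e^(−24λ)) / (12λ) = 1 − (0.1250 − 0.0156) / 2.079 = 0.947.
- If 10% of subjects contribute no follow-up: 40 × 0.9 × 0.947 = 34.1 events. This matches the stated 34.

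**Step 2: compute the interval at both levels.** The Brookmeyer-Crowley interval is the set of times t with |g(S(t)) − g(0.5)| ≤ z × se[g(S(t))], using the Greenwood variance. Here g is the identity for linear limits and log(−log) for log-log limits. z is 1.645 at 90% and 1.960 at 95%, a ratio of 1.19. Simulation of 10,000 trials under each of three readings of the 10% loss gave these means, in months:

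| 10% loss read as (mean events) | Limits | Lower, 90% → 95% | Upper, 90% → 95% | Width ratio |
|---|---|---|---|---|
| No follow-up (34.1) | log-log | 2.61 → 2.35 | 5.83 → 6.20 | 1.19 |
| No follow-up (34.1) | linear | 2.72 → 2.50 | 5.86 → 6.28 | 1.21 |
| Spread uniformly over follow-up (36.8) | log-log | 2.68 → 2.42 | 5.65 → 6.05 | 1.22 |
| Spread uniformly over follow-up (36.8) | linear | 2.69 → 2.61 | 5.84 → 6.06 | 1.10 |
| Exponential competing loss (34.6) | log-log | 2.66 → 2.38 | 5.76 → 6.14 | 1.21 |
| Exponential competing loss (34.6) | linear | 2.73 → 2.57 | 5.83 → 6.18 | 1.17 |

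The lower limit falls by 0.08 to 0.28 months and the mean width rises by 10% to 22%.

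**Step 3: compare with the plan's 2.5 months.** The 90% lower limits (2.61 to 2.73) are close to the stated value. In the reading that gives 34 events, however, linear limits at 95% give 2.50, which fits at least as well as log-log limits at 90% (2.61). The planning figure therefore does not show which level or transform was used, and checking results against it would not expose a wrong level.

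**Step 4: allow for the scan schedule.** Progression is seen only at scheduled scans (Weeks 9, 17 and 25, then every 12 weeks), taken as 56, 112 and 168 days after first dose and every 84 days after that. In 4,000 simulated trials for each of the first two loss readings:

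- The 90% and 95% lower limits fell on the same visit in 84-85% of trials (log-log) or 87-94% (linear).
- The whole interval was identical in 70-86% of trials.
- The mean lower-limit difference was 0.25-0.27 months (log-log) or 0.08-0.21 (linear), from jumps of a whole visit in a minority of trials.

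**The case against.** The strongest reply is that the plan already fixes the level. The protocol, the SAP text and the sample-size section all say 90%, and nothing specifies 95% for this endpoint. The sentence before the code names the 90% interval and says only that the production code will resemble the specimen. The specimen is plainly a skeleton, with no endpoint selection and no subgroup statement. SAP 7.1 refers to separate table, figure and listing specifications, which are not among the documents reviewed and might set the level. The default of 0.05 and the separate options for curve and quartile limits are software knowledge that the documents do not contain. An interval for the 1-year survival rate is itself an inference from SAP 7.4.1 and 7.4.2, because SAP 6.1.2 promises only the estimate.

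All of this is fair. It makes the mislabelled table a possibility and keeps the point small. It does not remove the gap: the one step printed as the source of the 90% interval does not contain the 90%, whatever the default may be.

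**Conclusion.** The concern holds, as a minor point. That the level is missing from the specimen can be read from the page. That the result would be 95% limits rests on the assumed default of 0.05 and on the specimen being used without a level added.

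If that happened, the interval would be too wide for its label. In the reading that gives 34 events, simulated coverage rises from 0.904 to 0.951 with log-log limits. Under the real scan schedule the two intervals would usually coincide. The error is conservative, the Kaplan-Meier median is unaffected, and no test or stopping rule uses the interval.

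**What to change.** In the SAP 7.4.1 specimen, set ALPHA=0.10 for the survival-curve limits and ALPHAQT=0.10 for the quartile limits where the SAS release has that separate option. Name the transform with CONFTYPE, since the table shows that linear and log-log limits differ. State that the same settings apply to overall survival and the 1-year rate, time to PSA progression, time to first subsequent antineoplastic therapy, the subgroup runs and the biomarker Kaplan-Meier medians.

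The cost is two or three options and one sentence, with no new data or analysis. SAP section 1 allows revisions until database hard lock.

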7.4.2 Analysis of Secondary Endpoints

Overall Survival, time to PSA progression, and time to first use of a subsequent antineoplastic therapy will be analyzed in the same manner as the primary endpoint.

PSA response rate (PSA30, PSA50, and PSA90) and objective response rate along with exact 90% confidence interval (Clopper-Pearson) will be calculated.

7.4.3 Analysis of Exploratory Endpoints

Unless otherwise noted, all continuous biomarker values will be summarized after log base 2 transformation. Descriptive statistics (e.g., N, mean, standard deviation, minimum, median, maximum for continuous variables; or N, frequency, and percentage for categorical variables) will be provided for baseline blood and plasma samples and by each post-baseline scheduled time point for the following endpoints;

1. AR-V7 (positive/negative status, continuous log base 2 for positive status only)
2. AR-V7 status change from baseline during the study (unchanged, positive to negative, negative to positive)
3. AR-V12/v567es (positive/negative status, continuous log base 2 for positive status only)
4. AR-V7 positive or AR-V12 positive (yes/no)
5. AR-FL (continuous log base 2)
6. Ratio of (log base 2 AR-V7)/(log base 2 AR-FL) (for positive status AR-V7)

7. GR-FL (continuous log base 2)
8. L702H (yes/no, only descriptive statistics)
9. W741C (yes/no, only descriptive statistics)
10. F876L (yes/no, only descriptive statistics)
11. T877A (yes/no, only descriptive statistics)
12. CTC detected (yes/no)
13. IL6 (continuous log base 2)
14. IL8 (continuous log base 2)
15. TNF- α (tumor necrotic factor alpha) (continuous log base 2)
16. sTNF R1 (soluble TNF receptor-1) (continuous log base 2)
17. CgA (chromogranin A) (categorical split TBD, continuous log base 2)
18. NSE (neuron specific enolase) (categorical split TBD, continuous log base 2)
19. Synaptophysin (categorical split TBD, continuous log base 2)

Three baseline binary AR predictors: 1) AR-V7 status; 2) a composite status (yes/no) of either AR-V7 positive or AR/V-12 positive; and 3) CTC status will be assessed individually, as independent variables, to predict rPFS, time to PSA progression, OS, and composite progression free survival (cPFS) using a single variable Cox model.

Multivariable AR Cox models will then be run on the same endpoints:

- 1) Using log base 2 transformed baseline AR-FL as a covariate in combination with baseline AR-V7 status;
- 2) Using log base 2 transformed baseline AR-FL as a covariate in combination with baseline composite AR-V7/V12 response;

Four baseline continuous log base 2 transformed inflammatory cytokine predictors: 1) IL6, 2) IL8, 3) TNF- α , and 4) sTNF R1 will be assessed individually, as independent variables, to predict rPFS, time to PSA progression, OS, and composite progression free survival (cPFS) using a single variable Cox model.

Three baseline continuous log base 2 transformed neuroendocrine predictors: 1) CgA, 2) NSE, and 3) synaptophysin will be assessed individually, as independent variables, to predict rPFS, time to PSA progression, OS, and composite progression free survival (cPFS) using a single variable Cox model.

Hazard ratio point estimates, n, standard errors, p-values, and 90% confidence intervals will be displayed in a single table for all the AR, inflammatory cytokine, and neuroendocrine Cox models.

KM plots, medians, and 90% confidence intervals for the binary AR predictors will be presented for rPFS, time to PSA progression, OS and cPFS.

Waterfall plot of maximum reduction in PSA from baseline with AR-v7, AR-v12, and AR mutation status labeled on the plot.

The AR-V7 and the composite AR-V7/V12 composite predictors will be individually assessed as an independent variables to predict PSA30, PSA50, PSA90, and objective response using Fisher's exact test. Note that objective response will be evaluated using subjects that are both BAS and have measureable disease.

Counts, frequencies, differences in frequencies and 90% Clopper-Pearson methodology will be displayed for the binary AR predictors.

Reported p-values for hazard ratios will use Wald (chi-square) test statistics, and p-values for comparing Kaplan-Meier curves will use log-rank (score) test statistics. Breslow method will be used for handling ties.

In the event that additional exploratory analyses are required for the Clinical Study Report, the SAP will be amended accordingly.

